13.0 Data Handling and Recordkeeping

13.1 Data Collection

The Investigator will utilize an electronic CRF for each subject. Entries made in eCRF must be verifiable against source documents; any discrepancies should be explained and documented. The Investigator will be responsible for reviewing all data and CRF entries and will sign and date the designated pages in each subject's CRF, verifying that the information is true and correct. The Investigator is responsible for the review and approval of all responses.

13.2 Data Management

All CRF data will be entered into a validated database maintained by the OU Clinical Trials Office (REDCap). REDCap (Research Electronic Data Capture) is a secure, web-based application designed to support data capture for research studies, providing 1) an intuitive interface for validated data entry; 2) audit trails for tracking data manipulation and export procedures; 3) automated export procedures for seamless data downloads to common statistical packages; and 4) procedures for importing data from external sources [21] All data entry, verification and validation will be performed in accordance with written standard operating procedures of the OU Clinical Trials Office. The database will be authorized for lock once all defined procedures are completed.

13.3 Data Privacy

The investigator must adhere to applicable data privacy laws and regulations. The investigator is responsible for ensuring that sensitive information is handled in

IRB NUMBER: 7488
IRB APPROVAL DATE: 11/23/2021

accordance with local requirements (e.g., Health Insurance Portability and Accountability Act of 1996 [HIPAA]). Appropriate consent and authorizations for use and disclosure and/or transfer (if applicable) of protected information must be obtained. Only the subject number and subject initials will be recorded in the CRF, and if the subject name appears on any other document (e.g., laboratory report), it must be obliterated on copies of the documents. The subjects will be informed that representatives of the Stephenson Cancer Center Data Safety Monitoring Committee, IRB, or regulatory authorities may inspect their medical records to verify the information collected, and that all personal information made available for inspection will be handled in strictest confidence and in accordance with local data protection laws.

**Protocol Number:**

**Grant Information:**

## **Abbreviations**

PFS	Progression free survival
SAP	Statistical analysis plan

## 1. Objectives

### a. Primary Objectives

1. To assess the treatment-related morbidity (including 30-day postoperative surgical morbidity and chemotherapy-related morbidity) and 1-year disease-free survival in patients with deficient serum 25(OH)D levels at the time of ovarian, primary peritoneal, or fallopian tube cancer diagnosis who did and did not receive vitamin D repletion.

### b. Major Secondary Objectives

1. To describe serum 25(OH)D levels, serum leptin levels, and VDR FokI SNP status among newly diagnosed ovarian, primary peritoneal, or fallopian tube cancer patients.
2. To determine the proportion of patients with ovarian, primary peritoneal, or fallopian tube cancer that have deficient vitamin D at diagnosis and have normal serum 25(OH)D after oral vitamin D supplementation during primary therapy.
3. To identify potential relationships between serum 25(OH)D and serum leptin levels when controlling for BMI.
4. To evaluate change of serum leptin levels with repletion of 25(OH)D in patients with low levels at the time of ovarian primary peritoneal, or fallopian tube cancer diagnosis.

### c. Translational Research Objectives

1. To evaluate VDR FokI SNP status relationship with serum 25(OH)D levels and treatment-related morbidity and cancer outcomes.

## 2. Design information

### a. General statistical considerations

This study will contain 2 cohorts, those with normal serum 25(OH)D and those with low serum 25(OH)D at enrollment. The study will take place in women with ovarian, primary peritoneal, and fallopian tube cancer, subsequently referred to as ovarian cancer in this document due to the overlap in disease and treatment.

Patients with low serum vitamin D levels, defined as <20 ng/mL, will be provided a supply of cholecalciferol (vitamin D3), 50,000 IU weekly for 8 weeks that will be dispensed in the Stephenson Cancer Center outpatient pharmacy to standardize therapy. They will then be provided with a prescription for 2,000 IU of cholecalciferol (vitamin D3) daily following completion of 8 weeks of therapy. Treatment with cholecalciferol will not impact initiation of treatment for ovarian cancer. Compliance with cholecalciferol repletion will be assessed with medication reconciliation at every gynecologic oncology visit.

### b. Sample Size and Power

The anticipated enrollment is 100 patients based on estimated new diagnoses of ovarian cancer treated in the Division of Gynecologic Oncology annually at the Stephenson Cancer Center. Based on the previously mentioned unpublished data, we presume that at least 25 of the prospectively enrolled patients will be vitamin D deficient. All of the vitamin D deficient women will be repleted with oral vitamin D. We will compare outcomes between these patients

and 75 vitamin D deficient ovarian cancer patients from previous years (these will include patients from the above-mentioned previous retrospective review as well as other patients with banked blood samples) using logistic regression. We will control for age, stage, and histology. With 25 prospective patients and 75 retrospective patients we will have 80% power to detect differences of 32% in chemotherapy delay between ovarian patients who were not vitamin D deficient (33%) and who were vitamin D deficient (65%).

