1.0 Hypothesis and Objectives

1.1 Specific hypotheses:

- 1.1.1 Low serum 25(OH)D will be associated with increased treatment-related morbidity.
- 1.1.2 Repletion of 25(OH)D will be associated with an increase towards normal of serum leptin levels.
- 1.1.3 VDR *FokI* SNP polymorphism will be associated with lower circulating levels of 25(OH)D.

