Figure 1. Serum 25(OH)D levels by chemotherapy delay status. Delay (≥ 7 days) n=30, median 25(OH)D 14.6 ng/dL. No delay n=28, median 25(OH)D 23.6 ng/dL (p=0.0112).

To date, there have been no prospective or randomized controlled trials evaluating serum 25(OH)D and treatment-related risks in cancer patients. No data exists regarding the effect of repletion of vitamin D and prevention of ovarian cancer treatment-related morbidity. As previously mentioned, number of cycles of chemotherapy received appears to correlate with improved OS in women with ovarian cancer [3]. Given the findings of the above-mentioned study correlating low serum 25(OH)D levels and chemotherapy

delay, vitamin D represents a potentially modifiable factor that could improve treatment tolerance among women with ovarian cancer.

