4.2 Inclusion Criteria (Prospective patients)

4.2.1 Patients must have a histologic diagnosis of ovarian, fallopian tube, or primary peritoneal carcinoma per pre-treatment biopsies by laparoscopy, or interventional radiology, paracentesis, or CT guided core biopsy. Histologic documentation of the original primary tumor is required via the pathology report.

4.2.2 Patients must have adequate:

4.2.2.1 Renal function: Glomerular Filtration Rate (GFR) ≥ 30 .

4.2.2.2 Gastrointestinal absorption: No underlying malabsorption syndrome (i.e. inflammatory bowel disease, celiac disease).

4.2.2.3 Ability to tolerate oral medication.

4.2.3 Patients taking vitamin D at the time of enrollment without a diagnosis of vitamin D deficiency.

4.2.4 Patients of childbearing potential must have a negative pregnancy test prior to the study entry and be practicing an effective form of contraception. If applicable, patients must discontinue breastfeeding prior to study entry.

4.2.5 Patients must have signed an IRB-approved informed consent and authorization permitting release of personal health information.

4.2.6 Patients must be at least 18 years old.

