4.3 Ineligible Patients

4.3.1 Patients with a known pre-existing diagnosis of vitamin D deficiency.

4.3.2 Patients with renal disease and a GFR < 30 .

4.3.3 Patients with primary hyperparathyroidism.

IRB NUMBER: 7488
IRB APPROVAL DATE: 11/23/2021

4.3.4 Patients with other invasive malignancies, with the exception of nonmelanoma skin cancer. Patients with concomitant endometrial cancer diagnosed at the time of their ovarian cancer are allowed to participate if the endometrial cancer is FIGO stage IB or less.

4.3.10 Patients of childbearing potential, not practicing adequate contraception, patients who are pregnant, or patients who are breastfeeding are not eligible for this trial.

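### The comparison of repleted women with historical controls does not adjust for baseline 25(OH)D, which the protocol links to the outcome and plans to measure in both cohorts

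*SAP*

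**What the plan says.** Protocol 12.0 and SAP 2b describe the same comparison. Prospectively enrolled women with low 25(OH)D, presumed to number at least 25, all receive vitamin D. Their outcomes are compared by logistic regression with those of 75 deficient women from earlier years who were not repleted. On covariates both documents say: "We will control for age, stage, and histology". The power statement follows: "With 25 prospective patients and 75 retrospective patients we will have 80% power to detect differences of 32% in chemotherapy delay", with rates of 33% and 65%.

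The logistic model appears only in this sample-size text. SAP section 6, which specifies the morbidity analysis, has descriptive statistics and a chi-square test, with no covariates.

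On 25(OH)D as a predictor, Protocol 1.1.1 states: "Low serum 25(OH)D will be associated with increased treatment-related morbidity". Protocol 2.2 and Figure 1 report an earlier study at the same university in women aged 65 and older. The median was 14.6 in 30 women with a chemotherapy delay and 23.6 in 28 without (p=0.0112).

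On measurement, Protocol 3.0 has 25(OH)D drawn at enrolment, before cancer treatment, from every prospective patient, and 25(OH)D evaluated in the controls' banked samples.

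**The concern.** Without randomisation, comparability of the two cohorts rests on restriction and on the covariates in the model. Restricting both cohorts to low 25(OH)D removes the contrast between deficient and normal women, but leaves differences in level below the cut-off. If level predicts chemotherapy delay, as the protocol hypothesises, a difference in average level between cohorts would be mixed into the estimated effect of repletion.

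Equal average levels cannot be presumed, because the cohorts are assembled by different routes. The treated women are below 20 ng/mL on a fresh enrolment sample. The controls are identified as low from tumour-bank samples of previous years, some of them from the earlier review of older women, and the cut-off is not restated for them. Depending on which cohort starts lower, the result would be an apparent benefit that is not there or a real benefit partly hidden.

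**Working it through.** **1. The plan's own figure.** Inputs from SAP 2b: 25 women at 33%, 75 at 65%. A two-sided 5% level is assumed, since none is stated.

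- Pooled rate = (25×0.33 + 75×0.65)/100 = 0.57.
- Null SE = √[0.57×0.43×(1/25 + 1/75)] = 0.1143.
- Alternative SE = √[0.33×0.67/25 + 0.65×0.35/75] = 0.1090.
- z = (0.32 − 1.96×0.1143)/0.1090 = 0.88, so power = 81.1%.

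The stated 80% is reproduced. The formula has no covariates, so it does not bear on which ones belong in the model.

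**2. Slope implied by the pilot.** Inputs from Protocol 2.2 and Figure 1: difference 23.6 − 14.6 = 9.0; n = 28 and 30; p = 0.0112. Assumptions: the medians stand for means, the p-value is from a t-test, the distributions are normal with equal SD, and the unit is ng/mL (the pilot prints ng/dL).

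- t on 56 df for p = 0.0112 is 2.623, so SE = 9.0/2.623 = 3.43.
- SD = 3.43/√(1/28 + 1/30) = 3.43/0.2628 = 13.06.
- Log-odds slope = 9.0/13.06² = 0.053 per ng/mL.

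**3. Bias from an assumed gap of 2 ng/mL, with no repletion effect.** Odds of delay at 65% = 0.65/0.35 = 1.857.

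- Treated women 2 ng/mL higher: odds ratio = exp(−0.0528×2) = 0.90; odds 1.671; delay 62.6% (−2.4 points).
- Treated women 2 ng/mL lower: odds ratio = exp(+0.0528×2) = 1.11; odds 2.064; delay 67.4% (+2.4 points).

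**4. Simulation that keeps levels below the cut-off.** 25 versus 75 women, true odds ratio 1, 4,000 runs per scenario. Control levels are centred at 13 ng/mL with SD 4.5 before truncation to 3–20 (assumed). Treated women are shifted upward before truncation. The models hold cohort alone, or cohort plus baseline 25(OH)D; age, stage and histology were not simulated.

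| Slope | Nominal shift | OR without / with 25(OH)D | False positives without / with |
|---|---|---|---|
| 0.053 | 2 | 0.95 / 1.02 | 5.0% / 5.2% |
| 0.053 | 4 | 0.89 / 1.02 | 5.5% / 4.4% |
| 0.10 (assumed) | 2 | 0.91 / 1.04 | 5.6% / 4.6% |
| 0.10 (assumed) | 4 | 0.80 / 1.03 | 7.4% / 4.8% |

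At the pilot slope, an odds ratio of 0.89 corresponds to a realised gap of about −ln(0.889)/0.053 = 2.2 ng/mL. Truncation roughly halves the nominal shift of 4. The delay rate becomes 62.3%, a change of 2.7 points.

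**5. Power cost of the extra covariate.** If baseline 25(OH)D explains a share R² of cohort membership (assumed), the effective size is multiplied by 1 − R². Pooled power goes from 81.1% to 80.2% (R² = 2%), 79.0% (5%) or 76.7% (10%). In the simulation at the planned effect and the pilot slope:

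- No imbalance: power 77.8% without the covariate and 78.5% with it.
- Nominal shift of 4: 85.1% without and 74.8% with. The higher figure includes the bias and is not a real gain.

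**The case against.** The strongest case against acting is that the design already restricts both cohorts to low 25(OH)D. That stands in part, and it is why the plausible bias is small. A mean gap of 5 ng/mL would give an odds ratio of 0.77 and about 6 points of delay (65% to 58.8%), but that is an extreme case when every level lies below 20.

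The slope is also fragile. It rests on medians read as means, spans the whole 25(OH)D range in women aged 65 and older, and is applied here below 20 ng/mL at all ages. With SD 13.06 and centre 14.6, a normal model puts about 13% of the delay group below zero. The figures show order of magnitude only.

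Adjustment could also go wrong. Prospective samples are run fresh and control samples are banked, and the documents do not say that the assays are comparable. A systematic difference would be confounded with cohort. This stands and shapes the fix.

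A reader might infer that the controls must be more deeply deficient, because Protocol 4.3 excludes "Patients with a known pre-existing diagnosis of vitamin D deficiency" and controls escape that rule. The documents do not show this. Only Protocol 4.2 is headed for prospective patients; 4.3 carries no such limit. Controls must also be unrepleted, and Protocol 2.3 calls repletion standard of care, which would tend to remove women with known deficiency from the controls too. For the same reason, a bias that always favours vitamin D cannot be inferred.

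**Conclusion.** The omission is real and worth correcting, but its likely effect is modest. A baseline variable that the protocol associates with the outcome, and plans to measure in both cohorts, is missing from the only adjusted model. The section that specifies the morbidity analysis has no adjustment at all. Under the assumptions above, a 2 ng/mL gap shifts delay by about 2.4 points from 65%, against a planned difference of 32. The shift may go either way, because no distribution of 25(OH)D by cohort is given.

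This does not show that the planned comparison is biased, or in which direction. It shows that a foreseeable source of bias is left open when the value needed to address it is already planned. Nor does it rest on 25(OH)D being a cause of morbidity: the protocol claims an association, and that is enough to justify adjustment.

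**What to change.** - In Protocol 12.0 and SAP 2b, add baseline 25(OH)D as a continuous covariate alongside age, stage and histology.
- In SAP section 6, name that adjusted logistic model as the morbidity comparison, so that it no longer stands only in the sample-size text beside an unadjusted chi-square.
- Report the distribution of baseline 25(OH)D by cohort.
- Report the model without 25(OH)D beside it, and state what is known about the comparability of banked and fresh assays.

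The cost is wording, one more parameter and a small loss of power: from 81% to about 77–80% if the covariate explains 2–10% of cohort membership (assumed). SAP section 9 allows no imputation, but few women should be lost, since a control cannot be classed as low without a measured value.

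The coding of stage and histology need not change for this. Treatment sequence (primary surgery or chemotherapy first) is a possible further covariate, because prospective women need a diagnosis "per pre-treatment biopsies by laparoscopy, or interventional radiology, paracentesis, or CT guided core biopsy" and no such rule is stated for controls. Consider it only if it is recorded for the controls; the protocol promises treatment-course data prospectively and does not say that it exists for the historical cohort.

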2.2 Vitamin D Deficiency in Cancer

Vitamin D has been well-studied due to its role in many important cellular pathways. Laboratory and observational studies suggest that it plays a role in many diseases such as autoimmune diseases, cardiovascular disease, diabetes, cancer risk and cancer survival. The correlation of low serum 25(OH)D with elevated risk for malignancy has been best studied in colorectal cancer [4]. Decreased levels of serum 25(OH)D have been correlated with increased risk of breast cancer in postmenopausal women. [5]. Women receiving chemotherapy and anti-hormonal therapy for breast cancer experience treatment-induced bone loss due to premature ovarian failure or direct cytotoxic effects of chemotherapy. This causes an increase in the osteoporosis and skeletal morbidity risk [6]. Similar effects can be estimated in ovarian cancer patients given that standard treatment requires surgical menopause as well as cytotoxic therapy in the majority of patients.

The majority of studies pertaining to vitamin D and ovarian cancer concern the association of low serum 25(OH)D with increased cancer risk. Limited study has been performed investigating the correlation of serum vitamin D and ovarian cancer prognosis or treatment-related morbidity. A study performed in Australia investigated serum 25(OH)D levels at the time of diagnosis of ovarian cancer in 670 women. They noted a significant association between higher circulating 25(OH)D concentrations and longer survival in women with ovarian cancer when adjusting for other clinical predictors of

survival [7]. Similarly, Walentowicz-Sadlecka et al. reported low serum 25(OH)D concentrations in women with ovarian cancer undergoing primary cytoreductive surgery to be associated with lower overall survival[8]. The impact of repletion of vitamin D in ovarian, primary peritoneal, or fallopian tube cancer patients has yet to be determined.

Findings from an unpublished study performed at the University of Oklahoma have shown an inverse correlation between low levels of serum vitamin D and treatment-related morbidity in women aged 65 years and older with ovarian cancer. More specifically, when comparing median serum 25(OH)D levels between patients who experienced chemotherapy delay ≥ 7 days versus those who did not, lower mean 25(OH)D levels were significantly associated with chemotherapy delays (23.6 ng/dL, n=28 no delay versus 14.6 ng/dL, n=30 delay, p=.0112). (Figure 1)[9].

[figure not shown]

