6.3 Sequence and timing of drug administration

Vitamin D deficient patients will receive oral cholecalciferol 50,000 IU weekly starting at the time of diagnosis of vitamin D deficiency. Initiation of cholecalciferol therapy will not delay initiation of standard treatment for ovarian cancer, nor will it preclude enrollment in other clinical trials. Therapeutic dosing at 50,000 IU will continue weekly for a total of 8 weeks. Patients will then be given a prescription for maintenance dosing 2,000 IU cholecalciferol thereafter.

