#### 6. Antitumor Evaluation

1. Treatment related morbidity (including 30-day postoperative surgical morbidity and chemotherapy-related morbidity) will be summarized by descriptive statistics as appropriate and compared across groups (chi-square for categorical variable).
2. Progression-Free Survival (PFS) at end of study (EOS) is defined as the time in months from first dose of the drug to the date of death or the first documented date of progression, whichever comes first. For patients who did not die and did not have progression, the PFS is censored at the last documented tumor assessment.

Survival curve for PFS will be generated using the Kaplan-Meier method. Median PFS with 95% CI will be computed.

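### The stated 80% power covers chemotherapy delay only, while the primary objective is broader and has no designated primary endpoint and no multiplicity rule

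*SAP*

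**What the plan says.** **Objective.** Protocol 1.2.1.1 and SAP 1a share one primary objective: to assess "treatment-related morbidity (including 30-day postoperative surgical morbidity and chemotherapy-related morbidity) and 1-year disease-free survival" in deficient women who were and were not repleted. It does not mention chemotherapy delay or rank its outcomes.

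**Sample size.** Protocol 12.0 and SAP 2b contain the only power statement: "With 25 prospective patients and 75 retrospective patients", "we will have 80% power to detect differences of 32% in chemotherapy delay". The two rates are 33% for women who were not deficient and 65% for women who were. The same paragraph says that the comparison with historical controls uses logistic regression controlling for age, stage and histology. Neither document states alpha or sidedness.

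**Place of delay among the outcomes.** Protocol 12.0 lists treatment delays, with completion of treatment, under treatment-related morbidity or mortality. The 7-day threshold appears only in the background, where Protocol 2.2 contrasts "patients who experienced chemotherapy delay ≥ 7 days versus those who did not".

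**Analysis.** SAP 6 says that treatment-related morbidity will be summarised and "compared across groups (chi-square for categorical variable"). It does not name delay or mention the logistic model. For progression-free survival it gives Kaplan-Meier curves and a median with a confidence interval. Among the SAP's analysis sections, delay is named only in section 7, for the comparison across genotype groups.

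**The concern.** The trial is sized on one binary outcome, but its primary objective is a group of outcomes that does not name it. A reader of the final report could not tell from the plan which result is the primary one, or whether the 80% stands behind it.

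Two things are at stake. If several outcomes are each tested at 0.05 and treated as primary, the chance of at least one false positive exceeds 5%. If alpha is divided to prevent that, the power for delay falls below 80%. In addition, an analyst who follows SAP 6 literally would run an unadjusted chi-square against historical controls, on morbidity outcomes for which the trial was not sized. Adjustment for age, stage and histology is the plan's only stated protection against differences between the 25 prospective and 75 retrospective women in those factors, and SAP 6 does not carry it through.

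**Working it through.** **Inputs.** From SAP 2b: n1 = 25 (repleted), n2 = 75 (historical), p1 = 0.33, p2 = 0.65. Assumption: two-sided alpha of 0.05, since none is stated.

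**1. Reproduce the 80%.** For the pooled two-proportion test,

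power = Φ{ [ |p1 − p2| − z·√(p̄(1 − p̄)(1/n1 + 1/n2)) ] / √(p1(1 − p1)/n1 + p2(1 − p2)/n2) }.

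- p̄ = (25 × 0.33 + 75 × 0.65)/100 = 0.57
- Null standard error = √(0.57 × 0.43 × (1/25 + 1/75)) = 0.1143
- Alternative standard error = √(0.33 × 0.67/25 + 0.65 × 0.35/75) = 0.1090
- Power = Φ[(0.32 − 1.960 × 0.1143)/0.1090] = Φ(0.88) = 81.1%

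Solving for sample size with the same test gives exactly 25 and 75. Enumerating the uncorrected chi-square exactly gives 82.1%. The stated figure is therefore sound for delay, as an unadjusted comparison at two-sided 0.05.

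**2. Family-wise error if each outcome is tested as primary at 0.05.** Under independence (assumption):

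- Two outcomes (morbidity; disease-free survival): 1 − 0.95² = 9.75%
- Three outcomes (surgical morbidity; chemotherapy morbidity; disease-free survival): 1 − 0.95³ = 14.3%

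**3. Power for delay if alpha is split equally.**

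| Alpha for delay | Pooled formula | Exact chi-square |
|---|---|---|
| 0.05 | 81.1% | 82.1% |
| 0.05/2 = 0.025 | 72.1% | 72.0% |
| 0.05/3 = 0.0167 | 66.4% | 67.6% |

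**4. Dependence on full reversal.** The 33% is the rate in non-deficient women, but the 25 women in the comparison are deficient and repleted. The calculation thus supposes that repletion brings delay all the way down to 33%. Holding controls at 65% and assuming smaller effects (exact chi-square, 0.05):

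| Delay rate after repletion | Power |
|---|---|
| 33% (plan) | 82.1% |
| 40% (assumed) | 61.1% |
| 45% (assumed) | 43.8% |

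**5. The other outcomes.** The documents give no event rates or hazard ratio for them, so their power cannot be computed from the plan. For illustration only, with 25 against 75 women, the pooled formula gives 17% power for surgical morbidity of 10% against 20%, and 44% for 20% against 40%. For disease-free survival, Φ(|ln HR|·√(d × 0.25 × 0.75) − 1.96) at a hazard ratio of 0.5 gives 38% with d = 30 events and 64% with d = 60. All these rates, hazard ratios and event counts are assumptions.

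**The case against.** Several stronger readings are tempting, and the documents do not support them.

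- **That the 80% has nothing to do with the primary objective.** Protocol 12.0 puts treatment delays within treatment-related morbidity, so the calculation addresses one component of the objective. For the same reason, the silence of SAP 6 on delay is a gap in specification and does not prove that delay goes untested; SAP 2b itself promises a logistic comparison of outcomes. This objection stands and limits the point.
- **That success on any one outcome would count as trial success.** No such rule is written. The objective is to assess, no alpha is stated, and SAP 6 gives no between-group test for progression-free survival. The objective can also be read as two outcomes, one with two named parts. The error rates in step 2 are therefore conditional: they apply only if the outcomes are each tested as primary, and they rest on independence between outcomes measured in the same women. Requiring every outcome to succeed, or treating the others as estimation, would not inflate the error.
- **That surgical and chemotherapy morbidity would be merged, diluting the effect.** Neither document defines such a composite. Protocol 12.0 says that both will be assessed.
- **That surgical morbidity precedes repletion.** Protocol 6.3 starts dosing when deficiency is diagnosed and says "Therapeutic dosing at 50,000 IU will continue weekly for a total of 8 weeks", without holding back cancer treatment. The timing of surgery is not given. At most, a 30-day postoperative window might close before the course is complete, and early chemotherapy cycles could fall in the same period.

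The sponsor could also say that a multiplicity rule or a declared hierarchy would resolve the ambiguity equally well. That is fair. What does not fall away is that the plan now has none of these.

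**Conclusion.** The point holds in a limited form. The 80% is arithmetically right for chemotherapy delay, and for that outcome only. The remaining parts of the primary objective have no stated power, no outcome is designated primary, and nothing controls multiplicity. The SAP's outcome section names neither the endpoint nor the adjusted model on which its own sample-size section relies.

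If the outcomes were each tested as primary at 0.05, family-wise error would be about 10% for two or 14% for three, under independence. An equal split would leave delay with about 72% or 68% power (exact chi-square). Even with delay as the sole primary endpoint, about 80% requires full reversal from 65% to 33%, and the figure is for an unadjusted test; the power of the adjusted model is not given. All figures assume two-sided 0.05. This should be changed: it decides what the trial can claim, and the remedy is small.

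**What to change.** 1. In Protocol 1.2.1, SAP 1a and SAP 6, name chemotherapy delay of 7 days or more (the definition in Protocol 2.2) as the single primary endpoint.
2. In SAP 6, compare repleted with unrepleted deficient women on that endpoint at two-sided 0.05, using the logistic model adjusted for age, stage and histology that SAP 2b already promises.
3. Make 30-day surgical morbidity, other chemotherapy-related morbidity and 1-year disease-free survival secondary, each analysed separately. If the sponsor prefers to keep them primary, state a hierarchy or alpha allocation and the resulting power for each.
4. In SAP 2b and Protocol 12.0, state that the 80% applies to delay only, is for an unadjusted two-proportion test at two-sided 0.05, and assumes that repletion lowers delay from 65% to the non-deficient rate of 33%. Show the power for smaller effects beside it.

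**Cost.** No new patients or outcomes are needed, since delays are already to be analysed, and treatment is unchanged. It does require a protocol amendment, because the primary objective changes. Surgical morbidity and 1-year disease-free survival lose primary status; neither has a stated power now.
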